#### 6.6 Prohibited Medications

Please consult the Medical Monitor with any questions pertaining to prohibited medications.

1. All cytotoxic agents, with the exception of hydroxyurea
2. All haematopoietic growth factors: romiplostim, eltrombopag, granulocyte and granulocyte-macrophage colony stimulating factor (G-CSF and GM-CSF) and erythropoietin (EPO)
3. Prednisone and prednisolone  $> 10$  mg/day (noted exception: use of corticosteroids for management of gout is allowed) and dexamethasone  $> 4$  mg/day. Maintenance supplemental corticosteroid therapy such as prednisone  $\leq 10$  mg/day or corticosteroid equivalent is allowed.
4. Monoamine oxidase A and B inhibitors
5. Anticoagulant and nonsteroidal anti-inflammatory drug (NSAID; including aspirin) use are prohibited in patients when their platelet count is  $< 50 \times 10^9/L$  (50 k/ $\mu L$ )

#### 6.7 Patients Who Terminate Early or Discontinue Study Medication

All patients who terminate the study early, or who discontinue IMG-7289 will be requested to return for follow-up visits, beginning with an End of Treatment visit as detailed in Section 9.6.1. If a patient refuses to enter follow-up, then an Early Termination visit should be performed as detailed in Section

9.6.3. Patients who discontinue IMG-7289 due to a DLT will be asked to undergo the EoT, Pre-EoS and EoS visits.

### **6.8 Treatment Failure**

MF patients not deriving clinical benefit (defined as not meeting progressive disease criteria as per Section 16.7 and safely tolerating IMG-7289), or who achieve complete response (CR), partial response (PR) or clinical improvement (CI) and subsequently relapse (Section 16.7), the equivalent of treatment failures, will discontinue IMG-7289 and undergo the EoT, pre-EoS and EoS visits.

## **7 STUDY TREATMENT**

### **7.1 Formulation, Labeling, Packaging and Storage**

#### **7.1.1 Formulation**

The drug product is IMG-7289, CCI [REDACTED]

[REDACTED] Details on capsules, including strengths, colours and sizes, can be found in the Pharmacy Manual.

The capsules will be manufactured in accordance with Annex 13 and principles of cGMP at:

Xcelience LLC  
[name]  
[name]

Changes to this section will be included *via* updates to the Pharmacy Manual and notification to sites, as appropriate.

#### **7.1.2 Packaging and Labeling**

IMG-7289 will be supplied to the site pharmacy department by Imago BioSciences (or designee) in bottles containing capsules in accordance with all applicable regulatory requirements.

Labels will also be in accordance with all applicable regulatory requirements for the labeling of active pharmaceutical ingredients and with Annex 13 of GMP. Labels will contain the drug name, protocol number, lot number, expiry date, storage conditions, name of the local Sponsor and a caution that the drug is for clinical trials use only.

#### **7.1.3 Storage**

The recommended long-term storage conditions for IMG-7289 is for the storage temperature not to exceed 25°C. IMG-7289 must be stored in a secure area with access limited to the Investigator and authorized staff and under the physical conditions that are consistent with IMG-7289-specific requirements. IMG-7289 supplies will be stored securely under the appropriate conditions according to the country, state and regional laws. Procedures for IMG-7289 storage and accountability will be detailed in a pharmacy manual.

## 7.2 Dispensing, Administration, Dosage and Missed Doses

### 7.2.1 Dispensing

All material supplied is for use only in this clinical study and should not be used for any other purpose. Only patients enrolled in the study may receive study drug, in accordance with all applicable regulatory requirements. Only authorized site staff may dispense study drug.

The Investigator is responsible for IMG-7289 accountability, reconciliation and record maintenance (Section 14.5). The Investigator must provide a prescription form every time drug is dispensed, including (but not limited to) the identification of the patient to whom drug is to be dispensed, the patient's weight, the requested dose in mg and the Investigator (or designee's) signature.

### 7.2.2 Administration

Appropriately trained personnel of the study site will provide instruction pertaining to IMG-7289 administration and supervise the administration of IMG-7289 on any day that it is taken in the clinic. With the exception of ITP Day 0, it is not required that IMG-7289 be taken in the clinic; this will be determined based on the patient's regular daily dosing time. When applicable, the date and time of each administration in the clinic will be recorded in the source notes.

IMG-7289 dosing will be based on the patient's ITP Day 0 weight. If during the study the patient's weight differs from ITP Day 0 by more than 10%, the amount of IMG-7289 dispensed should be corrected per the dose chart provided. In cases where using the ITP Day 0 weight is impractical for dispensing, a weight taken as close to ITP Day 0 as possible (e.g., Screening/Baseline) may be used; weight at a current visit may also occasionally need to be used. The source data must clearly document the weight used.

Patients should be instructed to:

- Take their IMG-7289 once daily, CCI [REDACTED]
- Swallow their IMG-7289 capsules whole, with a glass of water
- Take IMG-7289 on an empty stomach (fast for 1 hour prior to and 30 minutes after dose)

Patients may have clear liquids prior to their dose, and following study drug administration.

### 7.2.3 Dosage: Initial Treatment Period

In the ITP, all patients will be treated daily, for 169 days. Dosing will begin on Day 0 at a starting dose of IMG-7289 free base contingent on the protocol version the patient enrolled under. Details on the selection of and rationale for the starting dose and dosing schedule can be found in Section 3.6.

Through the use of dose titration, all patients will be dosed to the IMG-7289  $D_{pi}$ ; the dose needed to safely inhibit normal haematopoiesis for a *fraction* of the dosing cycle. At every visit, a haematology assessment will be performed for use in association with the Titration and Re-challenge Rules which are based on an evaluation of platelet, absolute neutrophil (ANC) and haemoglobin (Hgb) counts in comparison with results from the prior visit. Please refer to Section 7.2.3.1 for patients currently being treated under Amendment 5, and Section 7.2.3.2 for Amendment 6 details.

The  $D_{pi}$  is anticipated to be  $\leq 2$  mg/kg QD; however, this is not the upper limit for titration purposes as the dose needed to achieve a therapeutic effect will vary among patients and may change over time. The platelet titration target expected to be associated with a clinically significant therapeutic effect is:

- A platelet count of  $\geq 50$  to  $\leq 75$  k/ $\mu$ L ( $50-75 \times 10^9/L$ )

Please consult the medical monitor regarding dose modifications of IMG-7289 should an adverse event (AE) requiring a dose reduction occur, and also for the management of clinically significant changes in platelets, neutrophil counts, or other haematologic parameters.

CCI

CCI

CCI

CCI [redacted] purposes and to enable re-challenge to commence as soon as counts return to the required level, if safe to do so.

CCI

#### **7.2.4 Dosage: Additional Treatment Period**

For all patients entering a new Additional Treatment Period, dose titration will be per the Titration Rules in **Table 3**. Additional dose-titration may occur in consultation with the Medical Monitor.

#### **7.2.5 Missed Doses**

Patients who do not take their IMG-7289 dose at the usual required time should take it immediately upon noting that it was not taken; the patient should not take the dose more than 12 hours after the usual dosing time. If a patient misses a dose, they should not take two doses the following day, but should notify their study coordinator and continue with their normal daily dose the following day. For a dosing hiatus due to an SAE, please consult the Medical Monitor for guidance on re-start of dosing. Patients who miss an extended duration of IMG-7289 doses or exhibit serial non-compliance with treatment may be removed from the study at the discretion of the Sponsor.

#### **7.2.6 Interruption of Dosing**

Patients requiring a Dose Hold according to the Titration and Rechallenge Rules, or due to an (S)AE, should be monitored at least weekly for safety purposes and to enable re-challenge to commence as soon as counts return to the required level, if it safe to do so. During these visits, patients are required to undergo complete blood counts only.

### **8 DATA SAFETY MONITORING COMMITTEE (DSMC)/SAFETY ADVISORY BOARD (SAB) REVIEWS AND MANAGEMENT OF STUDY TOXICITIES, INCLUDING STOPPING RULES**

#### **8.1 Data Safety Monitoring Committee (DSMC)/Safety Advisory Board Reviews**

Safety will be monitored throughout the study in accordance with a Data Safety Monitoring Plan (DSMP)/Safety Advisory Board Plan (SABP) by a DSMC/SAB constituted by, at a minimum: the Imago BioSciences Principal Medical Monitor, the Coordinating/Lead Principal Investigator and an Independent designee, an AML clinical trials specialist with extensive clinical experience. The DSMC/SAB will provide recommendations regarding the conduct of the study and guidance to Investigators to ensure the safety and well-being of all participating patients. To do so, the DSMC/SAB will perform reviews at least quarterly of safety parameters and pharmacodynamic markers, to draw conclusions around the safety and pharmacodynamic effect of IMG-7289. DSMC responsibilities will remain in effect until the study has ended.

The DSMC/SAB will also review patient dose titrations and may recommend adjustments. At the original  $D_s$ , data from the first sentinel patient was reviewed by the DSMC/SAB prior to dosing the next sentinel patient. The DSMC/SAB convened within 4 days post-completion of 7 days of treatment for each of the sentinel patients at the original  $D_s$  and determined it was safe for:

1. Each sentinel patient to continue dosing, and
2. Additional patients to begin treatment with IMG-7289.

Additionally, the DSMC/SAB convened post-completion of 7 days of treatment of the required three patients at the new  $D_s$  and determined:

1. The safety of the new  $D_s$ , and
2. The ITP Day 3 (mid-week) visit could be removed from the visit schedule.

## 8.2 Management of Study Toxicities

Adverse event intensity will be evaluated using the National Cancer Institute (NCI) Common Terminology Criteria for Adverse Events (CTCAE) version 4.03, published 14 June 2010.

Dose-limiting toxicity and stopping rules are defined in Sections 8.2.2 and 8.2.3 below. Expected IMG-7289 toxicities based on non-clinical studies are reported in the latest available edition of the Investigator's Brochure.

### 8.2.1 Haematologic Toxicity

Haematologic values outside of the normal reference range are inherent features of MPNs, and are expected effects of many therapeutic attempts to manage these diseases.

Both genetic knockdown (KD) of LSD1 mRNA and pharmacologic inhibition of LSD1 show that the loss of LSD1 activity arrests the production of mature red cells, platelets and granulocytes while over-producing monocytes (Sprussel *et al.*, 2012; Kerényi *et al.*, 2013). Production of cells of lymphoid lineage, B and T cells is unimpaired indicating that LSD1 has very cell-specific functions and its inhibition also has very specific effects. LSD1 inhibition in malignant myeloid cells causes the induction of monocytic differentiation markers, as well as a reduction of self-renewal potential of neoplastic cells, all of which eventually result in apoptosis of treated cells. Thus, the anaemia, thrombocytopenia, neutropenia and monocytosis attending LSD1 inhibition, as observed in animals treated with IMG-7289, reflect primary pharmacodynamic effects. The kinetics of anaemia, thrombocytopenia, and neutropenia following complete LSD1 inhibition are a function of the lifespan of the individually affected cell types. Over the course of LSD1 inhibition, platelet and neutrophil counts are the most affected, reflecting their short mean lifespans of approximately seven and twelve days, respectively. Recovery of peripheral counts is reversible, rapid, and temporarily overshoots baseline haematologic values. At lower doses, the effects on haematopoiesis are much less pronounced suggesting that a modicum of residual LSD1 activity is sufficient to support blood cell formation. Thus, both the duration of LSD1 inhibition as well as the degree of inhibition are critical to the pharmacodynamic effects on myeloid lineages.

The intended dosing plan for MF patients is predicated on the observation that inhibition of LSD1 has a therapeutic effect when LSD1 is inhibited for a *fraction* of the 24 hour dosing cycle, sufficient to reduce platelets to a safe level while inhibiting to the greatest extent possible the production, by megakaryocytes, of cytokines and growth factors that drive bone marrow fibrogenesis and symptoms. The concentrations of IMG-7289 needed to achieve maximal effects on growth, differentiation and apoptosis *in vitro* with primary patient-derived malignant myeloid cells as well as *JAK2V617F* cell lines are similar to concentrations that *in vivo* inhibit red cell, platelet and granulocyte production. It is therefore expected that MF patients will require treatment at doses sufficient to reduce platelet counts and, to a lesser degree, absolute neutrophil counts. These reversible cytopenias can be managed clinically as needed with transfusions as well as broad-spectrum antibiotics in the case of febrile neutropenia, as are already standard practices in the routine management of malignant myeloid diseases.

The effects of IMG-7289 on normal myeloid haematopoiesis observed in non-clinical and clinical studies are expected in humans; these are pharmacodynamic effects of LSD1 inhibition by IMG-7289, thus not regarded as adverse. These events, with the exceptions below, will not be considered DLTs.

CCI

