**Definitions:**

*Haematologic Toxicity:* Haematologic values outside of the normal reference range are inherent features of MPNs, and are expected effects of many therapeutic attempts to manage these diseases. The effects of IMG-7289 on normal myeloid haematopoiesis observed in non-clinical and clinical studies are expected in humans; these are pharmacodynamic effects of LSD1 inhibition by IMG-7289, thus not regarded as adverse. These events, with the exceptions below, will not be considered DLTs.

*Dose limiting toxicity (DLT):* Any one of the following AEs that occurs through Day 7 of the Initial Treatment Period and is considered by the Investigator to be possibly, probably or definitely related to IMG-7289:

- Thrombocytopenia leading to clinically significant sequelae (i.e., a clinically significant bleeding event\* or the need for prophylactic transfusions);
- A clinically significant bleeding event\* in a patient with a platelet count  $> 50 \times 10^9/L$  (50 k/ $\mu$ L);
- Any Grade 4 or 5 non-haematologic adverse event;

- Any Grade 3 non-haematologic adverse event with failure to recover to Grade 2 within 7 days of drug cessation, with the following exceptions:
  - ≥ Grade 3 nausea, vomiting or diarrhea that responds to standard medical care
  - ≥ Grade 3 asthenia lasting less than 14 days
- Any Grade 3 electrolyte abnormality unrelated to the underlying malignancy and persisting greater than 24 hours.

\*A clinically significant bleeding event is defined as an event that is life-threatening, cannot be controlled and/or results in haemodynamic instability.

Patients who experience a DLT may have their dose adjusted downward if the Medical Monitor and Principal Investigator deem it safe for the patient to continue on IMG-7289.

Please consult the Medical Monitor for IMG-7289 dose modifications for the management of clinically significant changes in platelets, neutrophil counts, or other haematologic parameters.

Expected toxicities with IMG-7289 are reported in the latest edition of the Investigator's Brochure.

**Stopping Rules:** IMG-7289 will be discontinued in the event of the following:

- Post DLT, the Medical Monitor and Principal Investigator deem it unsafe for the patient to continue on IMG-7289.
- Post dose reduction due to DLT, the patient fails to demonstrate significant improvement within 21 days.

CCI

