## 11.2 Adverse Events

The Investigator is responsible for monitoring the safety of patients who have enrolled in the study and for accurately documenting and reporting information as described in this section. Patients will be instructed to report to the Investigator any AE that they experience. Investigators will ask about the occurrence of AEs at each visit. Investigators are required to document all AEs occurring during the clinical study, commencing with the first dose of IMG-7289 through to the End of Study Visit (scheduled at 28 days post last IMG-7289 dose). Adverse event recording will continue for patients who discontinue study treatment early but remain in follow-up, until their End of Treatment, Pre-End of Study and End of Study Visits have been completed.

Note: Any medical event which occurs from the time of Informed Consent but prior to dosing with IMG-7289 must still be documented in the patient's medical notes and will be recorded on the appropriate medical history eCRF pages.

**Note:** In the UK, serious AEs (SAEs) will be recorded from time of consent through the EoS or until the Investigator and Imago BioSciences determine that follow-up is no longer necessary.

Adverse events will be recorded on designated eCRF pages. Each AE is to be characterised (i.e., verbatim term) and information provided regarding its seriousness, start and stop dates, intensity, outcome, and causal relationship with the study drug.

An AE is any undesirable physical, psychological or behavioral effect experienced by a patient during participation in an investigational study, in conjunction with the use of the drug or biologic, whether or not product-related. This includes any untoward signs or symptoms experienced by the patient from the time of first dose with IMG-7289 until completion of the study.

Adverse events may include, but are not limited to:

- Subjective or objective symptoms spontaneously offered by the patient and/or observed by the Investigator or medical staff
- Findings at physical examinations
- Laboratory abnormalities of clinical significance

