Progression of underlying malignancy is not reported as an AE if it is consistent with the suspected progression of the underlying cancer. Clinical symptoms of progression may be reported as AEs if the symptom cannot be determined as exclusively due to the progression of the underlying malignancy or does not fit the expected pattern of progression for the disease under study. If there is any uncertainty about an AE being due to only the disease under study, it should be reported as an AE.

It is important Investigators record accurate AE terms in the eCRFs. Wherever possible, a specific disease or syndrome rather than individual associated signs, symptoms or laboratory parameter will be identified by the Investigator and recorded in the eCRF. However, if an observed or reported sign, symptom or laboratory parameter is not considered a component of a specific disease or syndrome by the Investigator, or is atypical, it should be recorded as a separate AE in the eCRF.

Disease signs, symptoms, and/or laboratory abnormalities already existing prior to the use of the investigational product are not considered AEs after treatment unless they reoccur after the patient has recovered from the preexisting condition or in the opinion of the Investigator they represent a clinically significant exacerbation in intensity or frequency.

Clinical significance is defined as any variation in signs, symptoms, or testing that has medical relevance and may result in an alteration in medical care. The Investigator will continue to monitor the patient until the assessment returns to Baseline or until the Investigator determines that follow-up is no longer medically necessary.

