### 11.2.2 Adverse Event Relatedness

The Investigator will make a judgment regarding whether or not, in his/her opinion, the AE was related to study drug. The Investigator will also evaluate any changes in laboratory values, make a determination as to whether the change is clinically significant, and whether or not the change(s) were related to study drug. However, even if the Investigator feels there is no relationship to the study drug, the AE or clinically significant laboratory abnormality MUST be recorded in the eCRF. Below are guidelines for relationship assessment:

- Unrelated: There was no relationship of the adverse event to the use of the drug or biologic. This may include, but is not limited to, the adverse experience being an expected outcome of a previously existing or concurrent disease, concomitant medication or procedure the subject experienced during their treatment period.
- Remote/Unlikely: Adverse events which are judged probably not related to the drug or biologic.
- Possible: There was no clear relationship of the adverse event to the use of the drug or biologic; however, one cannot definitively conclude that there was no relationship.
- Probable: While a clear relationship to the drug or biologic cannot be established, the event is associated with an expected adverse event (per the current Investigator Brochure or DSMC findings) or there is no other medical condition or intervention which would explain the occurrence of such an experience.
- Definite: The relationship of the use of the drug or biologic to the experience is considered definitively established.

If a causal relationship is considered probable, possible, or definite by the Investigator or Sponsor (dependent on the regional reporting requirements), the AE is considered to be “related” for purposes of regulatory reporting. If a causal relationship is considered remote/unlikely or unrelated, the AE is considered “unrelated” for purposes of regulatory reporting.

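### Protocol 8.2.1 and the Synopsis call the drug's blood-count effects not adverse, while 11.2 and 11.2.2 require clinically significant ones to be recorded, so cytopenia AEs and SAEs may be under-recorded

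*Protocol*

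**What the plan says.** Section 8.2.1 describes the drug's effects on normal myeloid blood-cell production and concludes that "these are pharmacodynamic effects of LSD1 inhibition by IMG-7289, thus not regarded as adverse". The Synopsis definitions repeat the sentence. A separate sentence follows: "These events, with the exceptions below, will not be considered DLTs". The exceptions therefore attach to DLT status. The Synopsis DLT definition, which is framed as a list of AEs, opens with "Thrombocytopenia leading to clinically significant sequelae".

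Section 11.2 sets out AE recording. It states that "Investigators are required to document all AEs occurring during the clinical study", and its examples of AEs include "Laboratory abnormalities of clinical significance". It defines clinical significance as "any variation in signs, symptoms, or testing that has medical relevance and may result in an alteration in medical care". Section 11.2.2 adds that, even where the investigator sees no link to the drug, "the AE or clinically significant laboratory abnormality MUST be recorded in the eCRF". Section 11.2.3 defines an SAE as an AE with one of a list of outcomes.

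The primary safety endpoint (Protocol 12.4.1, SAP III.A) combines AEs with changes in physical examination, vital signs and laboratory values. SAP IX.B builds its AE tables from the AEs reported on the eCRF.

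**The concern.** Lowering platelets is how the drug is titrated. Entry requires at least 100 x 10^9/L, the target is 50 to 75 x 10^9/L, and the titration rules are "based on an evaluation of platelet, absolute neutrophil (ANC) and haemoglobin (Hgb) counts". Cytopenia is thus the safety topic on which the recording rule matters most, and it is where the protocol gives two instructions. If some sites apply 8.2.1 as an exemption from AE recording, cytopenia AE, related-AE and graded-AE rates will be too low by an unknown amount. A cytopenia that is never treated as an AE also never reaches the seriousness assessment.

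**Working it through.** The plan states no figure on this point, so the check is mainly a comparison of texts.

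1. **Scope of the 8.2.1 sentence.** It has no threshold, grade or condition on sequelae. The DLT limit stands in the next sentence and does not govern it grammatically. The heading of Section 8.2 and that next sentence suggest that toxicity classification was meant, but the text does not say so.

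2. **Scope of 11.2 and 11.2.2.** Section 11.2.2 requires entry in the eCRF; it does not name the AE page. AE status comes from reading it with 11.2, where such abnormalities are among the things AEs may include. A count that leads to a dose hold, a dose reduction or a transfusion readily fits the definition of clinical significance. A count inside the titration target does not fit it merely by being below baseline.

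3. **Whether another visible passage settles it.** Section 11.2 expressly exempts disease progression from AE reporting but has no such exemption for cytopenias. It also defines an AE as an undesirable effect, and a site relying on 8.2.1 could say that an intended platelet fall is not undesirable. The Synopsis calls these effects not adverse and then places thrombocytopenia with sequelae in a list of AEs.

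4. **What the laboratory analysis recovers.** SAP IX.C plans values and changes by visit, maximum and minimum change from baseline, by-visit shifts by normal range and CTCAE grade, and an overall shift by clinical significance. SAP IX.G summarises transfusions. These do not depend on AE recording. The visible text gives no worst CTCAE grade per patient. By-visit summaries use expected visits, with windowing optional (SAP VI.J), while patients on a dose hold have blood counts at least weekly (Protocol 7.2.6). By-visit grade shifts can therefore miss a nadir, and none of these tables corrects the AE or SAE counts.

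5. **Arithmetic from the documents.** From the entry floor to target, the platelet fall is (100 − 75)/100 = 25% to (100 − 50)/100 = 50%, and more from a higher start. This is a change in count, not an AE rate. About 75 patients at about 25 sites is 75/25 = 3 per site, with no centre adjustment (SAP VI.E), so differences in site recording could hardly be detected in the AE data.

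6. **Illustration only.** Let p be the share of patients with a clinically significant cytopenia and q the share of those recorded as AEs. Neither is in the documents; both are assumptions. Reported incidence is p × q, with exact 95% intervals for N = 75:

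| p (assumed) | q (assumed) | Recorded patients | Reported incidence (95% CI) |
|---|---|---|---|
| any | 0% | 0 | 0% (0 to 4.8) |
| 20% | 100% | 75 × 0.20 = 15 | 20.0% (11.6 to 30.8) |
| 40% | 50% | 75 × 0.40 × 0.50 = 15 | 20.0% (11.6 to 30.8) |
| 40% | 100% | 75 × 0.40 = 30 | 40.0% (28.9 to 52.0) |
| 60% | 100% | 75 × 0.60 = 45 | 60.0% (48.0 to 71.1) |

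The second and third rows give the same reported result from different true rates. That is the practical difficulty: the AE table alone cannot show which applies.

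**The case against.** The strongest reply is that AE recording has its own section. Section 11.2 makes the investigator responsible for documenting and reporting as that section lays down, and 11.2.2 is mandatory. On this reading 8.2.1 says only that the expected effect is not adverse in itself, and a clinically significant abnormality is still recorded. The DLT list supports this by treating consequential thrombocytopenia as an AE. This has force. A reader might infer that one site could record every clinically significant cytopenia and another none, both in full compliance. The documents do not support that, because the second site would breach 11.2.2. What remains is that 8.2.1 contains an unqualified contrary statement, the Synopsis repeats it, and no visible text subordinates it to Section 11.

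A reader might also infer that the whole primary safety endpoint depends on site practice. It does not, because its laboratory component is captured regardless.

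The study is open-label with no comparator arm, so there is no between-arm bias. Under-recording would still distort the absolute rates, which are what a single-arm safety study reports.

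Finally, parts of Protocol 8.2.2 and 12.4.1 and of SAP IX.B are redacted, and the table shells and eCRF completion guidelines are separate documents. A reconciling rule or a worst-grade table could be in any of these, so its absence cannot be asserted firmly.

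**Conclusion.** The conflict is real and stands in the current text. Read literally, 8.2.1 and the Synopsis would take clinically significant cytopenias out of AE recording, and so out of SAE assessment, against 11.2 and 11.2.2. The effect is confined to the AE and SAE component of the primary safety endpoint.

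Its size cannot be derived from the documents. It is tempting to say that recorded thrombocytopenia could run from almost none to most patients at target, but that treats every on-target count as clinically significant, which the protocol's definition does not. The incidences tabulated above rest wholly on assumed values.

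The conclusion assumes that no redacted or separate text already settles the recording rule. On that basis the point should be corrected, given how central platelet reduction is to this drug and how little the correction costs.

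**What to change.** In Section 8.2.1 and the Synopsis, either delete the last five words of the sentence that calls these effects not adverse, or state that it concerns DLT classification only. Leave the next sentence unchanged, including its exceptions, since the DLT list depends on them. Add one sentence saying that Sections 11.2, 11.2.2 and 11.2.3 govern AE and SAE recording of cytopenias. If a redacted passage already says this, a cross-reference to it is enough.

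In SAP IX.C, add one table of worst on-treatment CTCAE grade per patient for platelets, absolute neutrophil count and haemoglobin, using all laboratory results including unscheduled and dose-hold counts. The table gives a safety estimate that does not depend on AE recording practice.

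The cost is a wording change, a reminder to sites and one table from data already collected. Reported cytopenia AE rates may rise. No dose, threshold or clinical rule changes.
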